The subjects' medical record will also be reviewed to determine whether any medical events of interest took place within the VA medical system. Medical events of interest include all-cause hospitalizations, emergency room visits, unplanned outpatient visits with medical providers, and medication changes. Study relevant data will be entered in the electronic case reports system.

[figure not shown]
We will access VHA's national Electronic Health Record (EHR) by way of CAPRI and/or JLV to determine health care costs.

**Figure 1.** LINK-HF response algorithm to the clinical alert

**Study Device:** The device (VitalConnect wearable patch, Figure 2) is a wearable adhesive Band-Aid-like multi-sensor that will be used to collect continuous vital sign data including; ECG, triaxial accelerometer, skin temperature and Impedance indicative of skin contact from patients (PhysIQ, Inc, Naperville, IL).

The devices communicate wirelessly, and information is then transmitted to a provided smart phone given for patient to use while on the study. The smart phone securely uploads the information to remote computers which automatically analyze the data and make results available to study investigators.

**Figure 2.** The VitalConnect wearable patch

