*Identification of prospective participants:* A “recruitment waiver” of the Health Insurance Portability and Accountability Act (HIPAA) authorization from the VA Central Institutional Review Board (CIRB) allows study personnel to screen for prospective participants using approved electronic health information files (corporate data warehouse), rolls of patients attending specific clinics, or medical records, with the assistance of local clinical informatics (IT) personnel as required.

Site study staff may contact a treating healthcare provider to explain the LINK-HF2 study and discuss whether the treating provider believes an identified prospective participant is suitable for participation in the study.

To minimize the possibility of coercion or undue influence. We will explain to the patients and clinicians that they are not obligated to participate in the study. Additionally, we will explain to them that should they choose to become a study participant, they can withdraw any time after enrollment. Furthermore, we will explain to the patient participants that if they decline to participate in the study, their medical care will not be impacted, and they will receive the same medical care as planned before.

To allow adequate time to exchange information and questions between the investigator and participant. We will ensure that the participants clearly understand the study procedure. We will spend adequate time with the participants, to address all questions and concerns the participants may have. Subjects are then scheduled at a mutually convenient time and enrolled.

**Risks:** This is a non-invasive monitoring system in which adhesive surface of a sensor device is placed on the skin of the chest. The possible risks from the device are:

1. Skin irritation due to subjects who may have an allergy to rubber, latex or Band-Aid-type adhesives may experience irritation at the placement of device.
2. Skin damage due to adhesives: Subjects with delicate or thin skin may have skin abrasions or tears when removing the disposable adhesive, The risk of adhesive issues are minimized by advising the patient on methods for safe removal, such as soaking the adhesive patch with hot water, use of rubbing alcohol to dissolve the adhesive, as well as slow and careful removal.

If the reaction is determined to be more than mild by the study team member or by the study patient, the adhesive / device will be removed, and the subject withdrawn from the study.

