## 5.5 Study Evaluations

Experimental procedures:

After enrollment, the patients will be followed-up per clinical protocol. The study coordinator will collect clinical information regarding patient's medical therapy and the outcomes of interest and submit via eCRFs. The information will be collected through CPRS, and the coordinator may ask clarifying information from the subjects during their clinical visits. If care for the patient is provided at a non-VA hospital while enrolled in the study, the subject will be asked to sign a release of information form and relevant data collected from the corresponding medical records.

The patients will be asked to complete a short version of the Kansas City Cardiomyopathy Questionnaire (KCCQ-12) and a visual analogue scale (VAS) at the time of enrollment, at 30 days and at 90 days after enrollment or study exit if different than 90 days  $\pm$  7 days.

Qualitative research:

Up to 20 subjects enrolled in the randomized study will participate in a semi-structured interview that will examine their experience with the study procedures as part of a qualitative research part of the study. The interview will last 30 to 60 minutes.

As part of implementation research, up to ten clinicians of SLC VAMC and up to ten clinicians in each participating site will be approached to participate as clinician participants in cognitive task analysis before subject enrollment starts and in semistructured interviews after subject enrollment has initiated. The interview will last 30 to 60 minutes.

Authorization documents/cover letters will be read to the participants before the interviews to confirm their willingness to participate in the interviews. The interviews will be audio-recorded, transcribed, and analyzed.

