## 5.6 Data Analysis

HF hospitalizations will serve as the primary outcome in a pivotal trial of the effect of the remote monitoring intervention. A key parameter for determining the statistical power in a pivotal trial of the effectiveness of the intervention for this outcome and other secondary outcomes is the proportion of subjects who meet the algorithm's criteria for an alert, and thus may potentially be affected by the intervention. The statistical power of the pivotal trial will also depend heavily on the proper functioning of the remote monitoring. Accordingly, data analyses of our study will estimate the following quantities:

- 1) The proportion of randomized patients who meet the algorithm's criteria for at least one alert;

- 2) The ratio of the number of days the remote monitor is functioning properly (patient wearing device and data quality sufficient to make the daily decision) to the total number of days in the study;
- 3) The rate of HF hospitalization, all-cause hospitalization and LOS for those hospitalized;
- 4) Standard deviations and serial correlations for PRO outcomes (KCCQ, VAS);
- 5) The proportions of patients for whom the KCCQ and VAS fall within subgroups defined by the clinical cutoffs 0-≤25, 25-≤50, 50-≤75, 75-≤100;
- 6) The proportion of randomized patients who are lost to follow-up prior to day 90.

The proportions in items 1, 5 and 6 will be computed in the full randomized cohort with exact binomial 95% confidence intervals (CI). We will also use estimates based on Kaplan-Meier curves (see below) to provide the proportions of subjects with at least one HF hospitalization in the 90 days after enrollment, the 90 days after end of monitoring and the first 180 days by randomized group, with 95% CI for these proportions within each intervention group and for the risk ratio between the intervention and control groups. The ratio of actual vs. intended intervention time the monitor is on and functioning properly will be expressed as the proportion of days the remote monitor is functioning properly, and will be displayed for the full cohort, by randomized group, and by clinical site using box plots and histograms. Summary statistics will be provided to summarize the ratio of actual vs. intended intervention time over the full intervention period. Standard deviations and serial correlations for the patient reported outcomes will be estimated.

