## Status and Event Questionnaire

The questionnaire will be read to the subject by a member of the study team during the clinic visit or telephone call, and answers will be recorded in the electronic case report system. The questionnaire identifies medical events that the subject can recall and report for the interval since the last inquiry, including events that occur at health care facilities outside the clinical setting of the investigator's site and which may otherwise be unknown to the site clinical staff. Events may include acute care utilization or adverse events, in which case AE/SAE evaluations are triggered.

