An Adverse Event is any undesirable experience (as judged by the principal investigator) associated with the use of a medical product in a subject that is not judged to be serious. The event will be deemed a Serious Adverse Event and should be reported to the IRB as such when the subject outcome is: Death, Life-threatening, Hospitalization (initial or prolonged), Disability or Permanent Damage, Required Intervention to Prevent Permanent Impairment, or other serious events as judged by the principal investigator. (See for reference FDA definition at:

<http://www.fda.gov/Safety/MedWatch/HowToReport/ucm053087.htm>)

All events shall be reported as per institutional guidelines.

Medical record request to non-VA hospital or emergency department or clinic

In the event that an acute care episode (a primary event) occurs at a non-VA facility, medical records will likely be provided to the clinical team. In the unlikely situation that this does not take place, the subject will be asked to sign a medical record release form, and the study team will obtain the records in question. Relevant data will be entered into the electronic case report system. A subject may also sign the medical record release at the time of consent to cover any possible outside admissions during enrollment.

Determination of Exacerbation timing/Cause

In the event that an acute care episode (a primary event) occurs and is determined to be an exacerbation of a subject's chronic conditions, the site PI will make a determination of the timing and cause of the exacerbation.

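### A more-than-mild skin reaction takes the subject out of the whole study, not only out of monitoring, and can needlessly lose outcome data that do not need the patch

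*Combined protocol and SAP*

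**What the plan says.** Section 5.2 (Risks) makes two things follow from a more-than-mild reaction: "the adhesive / device will be removed, and the subject withdrawn from the study". The rule is mandatory. The other device-related rules, for repeated loss of equipment (section 5.7) and for non-wear or poor data (section 6.0, Study Discontinuation), leave the decision to the study team.

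Four other places show how outcomes are collected:

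- **VA events.** Section 5.0 has the medical record reviewed to see "whether any medical events of interest took place within the VA medical system". No time limit is attached.
- **Non-VA events.** Section 5.5 provides for a release form and outside records with the condition "If care for the patient is provided at a non-VA hospital while enrolled in the study". Section 6.0 lets a subject sign the release at consent "to cover any possible outside admissions during enrollment". The Status and Event Questionnaire asks about outside events "which may otherwise be unknown to the site clinical staff".
- **KCCQ-12 and VAS.** Section 5.5 schedules them at enrollment and then "at 30 days and at 90 days after enrollment or study exit if different than 90 days".
- **Later follow-up.** Section 5.6 plans Kaplan-Meier estimates of HF hospitalization for the first 90 days, and also for "the 90 days after end of monitoring and the first 180 days by randomized group".

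**The concern.** Section 5.6 names HF hospitalization as the primary outcome of the future pivotal trial that this study is meant to inform. Hospitalizations, length of stay, KCCQ-12 and VAS come from records, contacts and questionnaires, so none of them requires the patch. The plan already follows HF hospitalization beyond the end of monitoring, so outcome data from subjects who no longer wear the device are part of the design.

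The rule nevertheless ends participation for a reason that the study device itself causes. Voluntary withdrawal is guaranteed elsewhere, so a subject who wants to leave can do so without it. What is at stake is some avoidable missing outcome data in randomized subjects. Loss to follow-up before day 90 (item 6 in section 5.6) may also come to include exits that the protocol created.

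**Working it through.** **1. What the rule loses, source by source**

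- *Non-VA hospitalizations.* The records provision and the release are both worded for the period of enrollment, and the questionnaire is a study contact. After withdrawal, nothing in the visible text keeps these routes open. Some events may still be seen, since section 6.0 expects outside records usually to reach the clinical team.
- *VA hospitalizations.* Record review after withdrawal is neither promised nor excluded.
- *KCCQ-12 and VAS.* One assessment at exit is kept; later scheduled ones are lost.
- *Alert status.* This needs the patch, so it is lost once the device is off, whatever the rule says.

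**2. The plan's own precision figures (section 5.6)**

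The half-width for a proportion at 0.5 is 1.96 × 0.5/√n:

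- n = 240: 0.063, as stated.
- n = 180 (25% loss): 0.073, as stated.

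**3. Number of subjects**

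No reaction rate is given, so 1% to 10% is an assumption: 240 × 0.01 = 2.4 and 240 × 0.10 = 24.

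Assume also that exits are spread evenly over days 0 to 90, and ignore the 7-day visit window. All affected subjects then miss the scheduled day-90 assessment (2.4 to 24). One third leave before day 30 and miss that one too (0.8 to 8). Each has one exit assessment instead.

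**4. Precision for HF hospitalization at day 90**

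Take reaction withdrawals as part of the 60 losses in the 25% allowance (240 − 180), and let the other losses contribute nothing. With m reaction cases, n = 180 + m. Under Kaplan-Meier a subject censored at exit still contributes time at risk until then.

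For a 50% day-90 risk, constant hazard and uniform exits, the large-sample Greenwood half-width is 1.96 × √(0.25 × I/n). Here w = m/n and I is the integral over u from 0 to 1 of ln 2 × exp(u ln 2)/(1 − w u). If the subjects are retained, I = 1.

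| Assumed rate | m | n | w | I | Censored at exit | Retained |
|---|---|---|---|---|---|---|
| 1% | 2.4 | 182.4 | 0.0132 | 1.0074 | 0.0728 | 0.0726 |
| 5% | 12 | 192 | 0.0625 | 1.0364 | 0.0720 | 0.0707 |
| 10% | 24 | 204 | 0.1176 | 1.0715 | 0.0710 | 0.0686 |

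The gain is about 0.0003 at 1% and 0.0024 at 10%.

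**The case against.** The best defence is that withdrawal may not end record collection at all. The consent form and HIPAA authorization, which would normally settle this, are not in the copy reviewed. The VA record review carries no enrollment limit, and the 180-day estimates imply that events are captured after the 90 days of participation. Outside records often reach the clinical team, and the exit assessment saves one KCCQ-12/VAS. All of this stands, and it limits the demonstrable loss to some non-VA events and some later questionnaires. It does not remove the point: the rule says that the subject leaves the study, and no visible text says that follow-up goes on. Nor does the rule hide the reactions themselves, because sensor adverse event rates go to the DSMB.

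Three stronger readings are tempting, and the documents do not support them.

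- *The withdrawn subjects contribute nothing to HF hospitalization.* A reader might then compare n = 180 with n = 204 and see the half-width fall from 0.073 to 0.069. The plan uses Kaplan-Meier, so the relevant comparison at 10% is 0.071 with 0.069, roughly half that gain.
- *The rule biases the comparison of arms.* Both arms wear the same patch and are subject to the same rule, so no between-arm bias is expected.
- *The denominator of the device-function ratio (item 2 in section 5.6) must be rewritten as part of this change.* That definition affects every early exit, including deaths. With an assumed 80% function while worn and exits spread evenly, moving from days in the study to the intended 90 days lowers the mean by 0.8 × p/2. At the planned 25% loss this is 0.8 × 0.25/2 = 0.10, against the plan's margin of 0.042. Section 5.6 may already intend the longer denominator, since it will "summarize the ratio of actual vs. intended intervention time over the full intervention period". This is a separate question.

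**Conclusion.** The point holds as a cheap improvement of low severity. The text supports the claim that a mandatory rule withdraws subjects from the study when stopping monitoring would be enough, and that this can cost non-VA hospitalization events and scheduled KCCQ-12/VAS assessments.

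The size rests on an assumed reaction rate of 1% to 10% (about 2 to 24 of 240 subjects), evenly spread exits, a worst-case 50% risk, and reaction cases counted within the 25% loss allowance. On those assumptions the precision gain is small throughout, and the alert proportion gains nothing. The reason to act is that the missing data are avoidable, not that the stated precision is at risk. Whether VA events are lost as well cannot be decided from the visible text.

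**What to change.** In section 5.2 (Risks), keep removal of the device. Replace the withdrawal clause with wording to this effect: monitoring stops and, unless consent is withdrawn, the subject remains in the study for the planned contacts, KCCQ-12/VAS and event questionnaires to day 90, and for the record review that supports the 180-day HF hospitalization estimates. Under Study Discontinuation in section 6.0, state that discontinuation for not wearing the device does not apply to these subjects. Leave the definition of item 2 out of this change.

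The cost is wording in two places. The contacts and questionnaires to day 90 are already scheduled. The record review to day 180 is implied for everyone by the planned estimates, although no procedure for it is set out in the visible text. The downside is continued data collection on a few subjects who no longer wear the device. If the consent form already provides for this follow-up, one sentence in section 5.2 saying so is enough.

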#### **Non-Experimental Implementation and Qualitative research:**

**Sample Size of qualitative part of the study:** As part of a qualitative research part of the study, a subset of up to twenty enrolled patients will be approached to participate in a semistructured interview that will examine their experience with the study procedures. In addition, up to ten clinicians of SLC VAMC and up to ten clinicians in each participating site will be approached to participate as clinician participants in semi-structured interviews that will be part of the implementation process and integration of remote monitoring into the clinical workflow at SLC VAMC.

Participants in the experimental part of the study will be approached during follow-up appointments to see if they are interested in participating in semi-structured interviews. The interviews will be explained to the patients. The interviews will be scheduled, and authorization documents/information sheets will be read to the subjects immediately before the interviews to confirm their willingness to participate in the interviews.

Up to 10 clinicians/site on the HF team will be approached to participate as clinician participants in cognitive task analysis interviews before subject enrollment starts and in semi-structured interviews after subject enrollment has initiated. Authorization documents/information sheets will be read to the participants immediately before the interviews to confirm their willingness to participate in the interviews.

**Risks:** The risks are mostly limited to the possible loss of confidentiality since the interviews will be recorded. All appropriate precautions are being made to preserve confidentiality.

**Benefits:** There will be no immediate direct benefit to participants. On a system level, this research will help implementation of the studied approach to clinical workflow.

**Confidentiality:** All study patient data will be stored both on paper and electronically on secured, password-protected computer systems in physically locked facilities at the VA and at PhysIQ offices. The only people who will have authorized access to any of this data are the investigative medical staff at the VA hospital, and authorized personnel of PhysIQ, all of whom have been certified under patient confidentiality training.

The information collected for this study will be kept confidential. There will be no photographs or videos of the interview. Transcription services will be provided by VA Centralized Transcription Service Program (CTSP). All identifying information will be removed during the transcription process. All care provider data and interview recordings and transcripts will be stored both on paper and electronically on secured, password-protected computer systems in physically locked facilities at the VA offices. The only people who will have authorized access to any of this data are the investigative medical staff at the VA hospital and the study operational partner PhysIQ.

All research staff having access to study data have completed the VA Privacy and HIPAA training and the VA Privacy and Information Security Awareness and Rules of Behavior training within the past twelve months which will be locked at all times with access available only to the investigator team.

## 5.3 Informed Consent Procedures

### CONSENT PROCESS

The potential participants who meet inclusion/exclusion criteria will be approached a few days before discharge from the hospital or at the time of their routine follow-up clinic visit at the Heart Failure Clinic. After the participants consent to join the study, the non-invasive monitoring device will be fitted to the patients. Once the patients give their verbal consent, we will obtain their written consent immediately afterwards as well. Therefore, there will be no waiting period between the consent process and the procurement of written consent. The patients will be free to ask about any details pertinent to the study. They will also be allowed several hours, if needed, to discuss with family and significant others before making the decision to participate.

We will explain to the patients that they are not obligated to participate in the study. Additionally, we will explain to them that should they choose to become a study participant, they can withdraw any time after enrollment. Furthermore, we will explain to the patients that if they refuse to participate in the study, their medical care will not be impacted, and they will receive the same medical care as planned before.

We will ensure that the patients clearly understand the study procedure. We will spend adequate time with the participants, to address all questions and concerns the patients may have. Subjects are scheduled at mutually convenient time and enrolled. Their time is not a limitation. In the event we are

unable to continue using a hospital room for research purposes we will take the individual(s) over to the outpatient area prior to leaving the facility.

For the subset of enrolled patients and for clinicians participating in semi-structured interviews as part of implementation and qualitative research, authorization documents/cover letters will be read before the interviews to confirm their willingness to participate in the interviews.

## **SPECIAL INSTRUCTIONS AND DEFINITIONS OF EVALUATIONS**

### **Informed Consent**

Informed consent must be documented per local regulation. Documentation of consent must be noted in the subject's medical record and/or the original signed consent must be available for review. Consent will be additionally confirmed in an eCRF. Reconfirmation of consent should be verbally checked at every subsequent interaction. Withdrawal of consent shall be documented in the subject's record and in compliance with local regulations.

